**3.3.2 FDA Procedural Success (at 1 month): Safety**

- Device Success, and
- None of the following device or procedure related SAE's:
  - a) Life threatening bleeding
  - b) Major vascular or cardiac structural complications requiring intervention,
  - c) Pericardial effusion requiring drainage or surgery (includes tamponade),
  - d) Stage 2 or 3 AKI (includes new dialysis).
  - e) Severe heart failure or hypotension requiring IV inotrope, ultrafiltration or MCS.
  - f) Prolonged intubation > 48 hours

**3.3.3 FDA Individual Patient Success (at 6-months & 1 year): Effectiveness**

- Device Success and all of the following:
  - a) No re-hospitalizations or re-interventions for the underlying condition (e.g. HF or TR)
  - b) Improvement vs. baseline in symptoms (e.g. NYHA Class improves from baseline)
  - c) Improvement vs. baseline in functional status (e.g. 6MWT improves from baseline)
  - d) Improvement vs. baseline in QoL (e.g. SF-12, KCCQ improves from baseline)

**3.4 Other Endpoint: Echocardiographic parameters**

A. Reduction in TR severity (assessed by TR grade and quantitative measures) as assessed by TEE pre- and post-implant in the procedure room.

Additional echocardiographic parameters will be compared to baseline:

B. TTE parameters assessed at baseline, discharge, 30 days, 6 months, 1 year and annually until 3 years post procedure.

Revision Date: April 1, 2019

Rev

3.0

For Use Only by  
Affiliates of Edwards  
Lifesciences

Page 11 of 18

Title

Statistical Analysis Plan for FORMA EFS

1. TR grade- qualitative assessment
2. Vena Contracta (2D)
3. EROA (PISA/2D or 3D/3D color doppler)
4. Regurgitant volume
5. Tricuspid annular diameter (end-diastolic – S-L)
6. Tricuspid annular area (2D/3D mid-diastolic)
7. Tenting area and distance
8. Forward stroke volume
9. RV dimensions
10. Right atria volume
11. Left ventricular Ejection Fraction
12. Inferior Vena Cava dimensions/respiratory variations
13. Hepatic vein flow reversal
14. Pulmonary artery pressure (peak)
15. Right ventricular function

Final

 Edwards	Revision Date: April 1, 2019		Rev	3.0	For Use Only by Affiliates of Edwards Lifesciences	Page 12 of 18
	Title	Statistical Analysis Plan for FORMA EFS				

#### **4. ANALYSIS POPULATIONS**

This clinical study will enroll 60 patients. This sample size was established based on typical sample sizes for early feasibility studies and no statistical justification was utilized.

It was decided that from an analysis perspective, data from the first 30 patients (patient enrolled before Rev L) and second 30 patients (Patient enrolled under Rev L and after) will be analyzed together and also separately by sub-groups of before rev L and rev L and after, where applicable.

The analysis population will be grouped into three analysis cohorts that in total comprise all the patients in whom the study procedure has been attempted (vascular access obtained) in this study. The analysis cohorts are defined below:

##### **4.1 Intent-to-Treat (ITT) Population**

The Intention-to-Treat (ITT) population includes all patients who signed informed consent, met eligibility criteria, and in whom the study procedure has been attempted (i.e. at least skin incision to introduce the FORMA System).

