8.7.1 VISIT & ASSESSMENT WINDOWS

Post-procedure follow up visits will be performed on all implanted study patients at 1 month, 6 months, and annually for 3 years post implant procedure intervals as illustrated in Table 11 below:

Table 11 – Follow-up Visit Windows

| Scheduled Follow-up Interval | Follow-up Window |
|-----------------------------------|------------------|
| 1 month (30 days) | ± 7 days |
| 6 months (180 days) | ± 30 days |
| Annually (365 days) up to 3 years | ± 45 days |

Table 12: Screening/Baseline Assessment Windows

| Assessment | Window |
|------------------------------------|--|
| TTE* | Within 60 days of submission to Sponsor |
| TEE** | Within 90 days of submission to Sponsor |
| Hemodynamic Monitoring | Within 90 days of scheduled implant procedure ⁷ |
| Venogram (pacemaker lead patients) | Within 90 days of scheduled implant procedure if venous patency cannot be determined by CT |
| CT Angiogram** | Within 180 days of submission to Sponsor |
| Coronary Angiogram | Within 180 days of scheduled implant procedure |
| Pacemaker interrogation | Within 180 days of scheduled implant procedure |

* TTE must be conducted after informed consent and must be collected according to echo core lab acquisition protocol.

**pre-existing TEE/CT image of adequate quality capturing required anatomy for assessment can be used.

Note: For all imaging (TTE, TEE, CT angiogram, coronary angiogram), if imaging is deemed incomplete or inadequate for assessment, repeat imaging may be required.

Note: Procedure should be scheduled within 90 days of consent.

During the follow up visits, medical information, findings and results will be entered in the appropriate electronic case report forms.

Study patients who have signed the Informed Consent, have met all eligibility criteria, and have the study procedure attempted (at least skin incision to introduce the FORMA system) are considered enrolled in the study.

Patients who enter the procedure room but who do not have the study procedure attempted (at least skin incision to introduce the FORMA system) will be classified as

⁷ If the screening echo confirms the PAP meets the study criteria, the right heart catheterization/hemodynamic assessment at the baseline evaluation may be waived.

“non-implanted” and will be followed 30 days for safety. These patients will be exempt from all other study follow up visit procedures.

Final

Table 13 – Summary of Required Study Procedures

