13.2 ANALYSIS POPULATION

Analysis populations are defined below:

- **Intent-to-treat population**
The intention-to-treat (ITT) population includes all patients who signed informed consent, met eligibility criteria, and in whom the study procedure has been attempted (i.e. at least skin incision to introduce the FORMA System).
- **As-treated population**
The as-treated population is a subset of ITT population and includes all patients in whom the study device is implanted and remains in position at the time of the patient's exit from the procedure room.
- **Per-protocol population**
The per-protocol (PP) population is a subset of as-treated (implanted) population in whom there are no inclusion/exclusion criteria-related protocol deviations.

The as-treated population will be the primary analysis population for performance and safety assessment. The ITT population will be used for device success, and additional safety analysis. Additional analyses of performance and safety data using the PP population will also be performed, if there is a clinically meaningful difference in sample size from the as-treated population.

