##### **4.2 As-Treated (AT) Population**

The As-Treated population (AT) is a subset of the ITT population and includes all patients in whom the study device is implanted and remains in position at the time of the patient's exit from the procedure room.

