##### **4.3 Per-protocol Population**

The Per-Protocol (PP) population is a subset of the As-Treated (implanted) population in whom there are no inclusion/exclusion criteria-related protocol deviations.

The AT population will be the primary analysis population for performance and safety assessment. The ITT population will be used for device success, and additional safety analyses. Additional analyses of performance and safety data using the PP population will also be performed, if there is a clinically meaningful difference in sample size from the as-treated population.

 Edwards	Revision Date: April 1, 2019		Rev	3.0	For Use Only by Affiliates of Edwards Lifesciences	Page 13 of 18
	Title	Statistical Analysis Plan for FORMA EFS				

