## 8. ANALYSIS OF STUDY ENDPOINTS

### 8.1 Safety Endpoint

Safety will be analyzed as a composite endpoint of Major Adverse Events (MAEs) at 30 days.

The MAE endpoint and its components will be summarized by counts and percentage for the AT cohort. Data Monitoring Committee (DMC) adjudicated data will be used in the analysis.

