#### 8.4.3 Additional Safety Analysis

Site-reported adverse events (AEs) and serious adverse events (SAEs) will be summarized by early events ( $\leq 30$  days) and late events ( $> 30$  days) for the ITT cohort. In addition, a listing of all the AEs and SAEs for the entire study population will be provided.

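### The eligibility condition in the ITT definition, read literally, leaves a treated patient who failed a criterion out of ITT, AT and PP, contrary to SAP section 4

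*SAP*

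**What the plan says.** SAP section 4 introduces three cohorts that "in total comprise all the patients in whom the study procedure has been attempted (vascular access obtained) in this study". That sentence carries no eligibility condition.

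The definitions that follow are nested:

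- **ITT** (SAP 4.1): "includes all patients who signed informed consent, met eligibility criteria, and in whom the study procedure has been attempted". Protocol 13.2 sets the same conditions: "signed informed consent, met eligibility criteria, and in whom the study procedure has been attempted".
- **AT** (SAP 4.2): "is a subset of the ITT population and includes all patients in whom the study device is implanted", with the device still in position when the patient leaves the procedure room.
- **PP** (SAP 4.3): a "subset of the As-Treated (implanted) population in whom there are no inclusion/exclusion criteria-related protocol deviations".

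AT is the primary population for performance and safety. SAP 8.1 states: "The MAE endpoint and its components will be summarized by counts and percentage for the AT cohort". In SAP 8.2, device success uses ITT and AT, and procedural and clinical success use AT. In SAP 8.4.2, Kaplan-Meier time to first heart failure rehospitalization uses AT. In SAP 8.4.3, early and late AEs and SAEs are summarized "for the ITT cohort. In addition, a listing of all the AEs and SAEs for the entire study population will be provided".

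The protocol defines enrolment in two ways. Section 8.7.1 says that consented patients who "have met all eligibility criteria, and have the study procedure attempted (at least skin incision to introduce the FORMA system) are considered enrolled". Section 8.2 places enrolment at skin incision, after the patient has been judged eligible. Section 14.3 lists treating a patient who did not meet the eligibility criteria at the time of implant as a major deviation.

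**The concern.** Eligibility is a condition of the outermost cohort, so failing a criterion removes a patient from every cohort. Section 14.3 shows that the protocol foresees such a patient. Whether someone exposed to the device counts in the safety denominator then depends on whether *met* refers to actual status or to a judgement made before the procedure.

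Two things are at stake. First, on the literal reading an exposed patient is absent from the main safety endpoint and from the AE/SAE summaries, in a study whose first objective is to evaluate safety and function. Second, PP loses most of its function. If everyone in AT already met the criteria, a failed criterion can never separate PP from AT. The two could then differ only through other eligibility-related deviations, such as a missed or out-of-window screening assessment. SAP 4.3 runs PP analyses only if PP and AT differ meaningfully in size, so they would rarely be triggered.

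**Working it through.** The plan states no figure on this point to reproduce. The sample size of 60 has no statistical derivation (Protocol 13.1, SAP 2.3). The check is one of set membership, followed by an illustration of size.

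**Step 1: the rules as written, for consented patients with the procedure attempted**

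- ITT = eligibility met
- AT = ITT and implanted
- PP = AT and no inclusion/exclusion deviation

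PP lies inside AT and AT inside ITT, so the union of the three is ITT itself. A patient who failed a criterion necessarily has an inclusion/exclusion deviation, which leaves six possible patterns:

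| Eligibility met | Implanted | I/E deviation | ITT | AT | PP | Covered by SAP 4 opening |
|---|---|---|---|---|---|---|
| yes | yes | no | yes | yes | yes | yes |
| yes | yes | yes | yes | yes | no | yes |
| yes | no | no | yes | no | no | yes |
| yes | no | yes | yes | no | no | yes |
| no | yes | yes | no | no | no | yes |
| no | no | yes | no | no | no | yes |

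The last two rows are the contradiction: SAP section 4 counts these patients, and SAP 4.1 to 4.3 place them nowhere.

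**Step 2: outputs affected on the literal reading**

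The patient is omitted from the 30-day MAE endpoint, all three performance endpoints, Kaplan-Meier time to first heart failure rehospitalization, and the early and late AE/SAE summaries. The patient may still appear in the AE/SAE listing, whose population is not defined, and in outputs that name no cohort: the FDA endpoints (SAP 8.3), the echocardiographic parameters (SAP 8.4.1) and parts of SAP 8.4.2.

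**Step 3: illustration of size**

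Assumptions, none of them from the documents: 60 patients implanted, *k* of them ineligible, 6 MAEs among the eligible.

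- Reported rate = 6/(60 − *k*).
- Rate with everyone included = 6/60 if no ineligible patient has an MAE, up to (6 + *k*)/60 if each has one.
- Intervals are 95% Clopper-Pearson, the method in SAP 6.1.

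| *k* | Reported | All 60, lowest | All 60, highest | Shift (points) |
|---|---|---|---|---|
| 1 | 6/59 = 10.2% (3.8–20.8) | 6/60 = 10.0% (3.8–20.5) | 7/60 = 11.7% (4.8–22.6) | −0.2 to +1.5 |
| 3 | 6/57 = 10.5% (4.0–21.5) | 6/60 = 10.0% (3.8–20.5) | 9/60 = 15.0% (7.1–26.6) | −0.5 to +4.5 |
| 5 | 6/55 = 10.9% (4.1–22.2) | 6/60 = 10.0% (3.8–20.5) | 11/60 = 18.3% (9.5–30.4) | −0.9 to +7.4 |

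The effect can go either way. With *k* = 0 nothing changes.

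**Step 4: after the change**

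If ITT requires only consent and an attempted procedure, all six patterns fall in ITT. The implanted ineligible patient is in ITT and AT but not PP, and the total agrees with the opening of SAP section 4.

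**The case against.** The strongest reply is that the authors probably meant eligible as judged before the procedure. Protocol 8.2 and the Enrollment entry in Protocol section 18 treat eligibility as a determination made beforehand. The PP rule takes eligibility deviations out of AT, which presupposes that such patients are in AT. SAP section 9 says the PP definition was changed in protocol Rev M and carried into this SAP, so it is deliberate text. On that reading the passages fit together. This has force as evidence of intent. It does not settle the matter: no sentence says so, and Protocol 14.3 uses the same verb for actual status at implant. What stands is that this is ambiguous wording, and it does not show that patients would in fact be dropped.

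The consequences are also limited. There is no test or performance goal, all AEs and SAEs are to be listed, the sponsor and DMC monitor all safety data, and an ineligible treatment is a reportable deviation. That is right, and it bounds the severity. A listing still does not restore a patient to a rate or its denominator.

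The larger illustrations are extreme. The upper figure at *k* = 5 needs every ineligible patient to have an MAE, and sponsor review of pre-procedure imaging makes many ineligible treatments less likely. This too is fair. The one-patient shift lies well inside its own interval, and the *k* = 5 row should be read only as an outer bound.

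Finally, cohort membership does not use the definition of enrolled in Protocol 8.7.1, so that edit is not strictly needed. It is an alignment with Protocol 8.2 and does no harm.

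**Conclusion.** The concern holds as a conflict in the text and should be fixed. SAP 4.1 and Protocol 13.2, read literally, exclude from all three cohorts a treated patient whom SAP section 4 says they contain. The documents do not state which reading governs.

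The effect on results depends on the number of ineligible treated patients, which the documents do not give and which may be zero. Under the assumptions above, one such patient shifts the MAE rate by −0.2 to +1.5 points and three by −0.5 to +4.5 points. No pass/fail conclusion is affected. Rates and denominators are, and in a descriptive study meant to guide future designs they are the main product.

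**What to change.** Delete the eligibility condition from the ITT definition in SAP 4.1 and Protocol 13.2, and the matching condition from the definition of enrolled in Protocol 8.7.1. ITT is then every consented patient with at least a skin incision to introduce the system. AT is those with the device implanted and in position at exit. PP alone removes inclusion/exclusion deviations. This agrees with SAP section 4 and gives the same result under either reading of *met*.

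The cost is one clause in three places. The two protocol edits need a written amendment under Protocol 16.5. No new data or visits are required. The trade-off is that ineligible treated patients then count in the safety and performance tables, with PP showing results without those patients.

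A lesser option is one sentence in SAP 4.1 saying that the condition means judged eligible before the procedure, and that deviations found later affect PP only. It avoids an amendment but leaves the protocol wording open.

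Two optional tidy-ups: use one term for an attempted procedure (SAP section 4 refers to vascular access, SAP 4.1 to skin incision), and state which patients the AE/SAE listing in SAP 8.4.3 covers, since Protocol 12.2 monitors adverse events from consent.

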##### **4.2 As-Treated (AT) Population**

The As-Treated population (AT) is a subset of the ITT population and includes all patients in whom the study device is implanted and remains in position at the time of the patient's exit from the procedure room.

##### **4.3 Per-protocol Population**

The Per-Protocol (PP) population is a subset of the As-Treated (implanted) population in whom there are no inclusion/exclusion criteria-related protocol deviations.

The AT population will be the primary analysis population for performance and safety assessment. The ITT population will be used for device success, and additional safety analyses. Additional analyses of performance and safety data using the PP population will also be performed, if there is a clinically meaningful difference in sample size from the as-treated population.

 Edwards	Revision Date: April 1, 2019		Rev	3.0	For Use Only by Affiliates of Edwards Lifesciences	Page 13 of 18
	Title	Statistical Analysis Plan for FORMA EFS				

## 5. DEFINITIONS

### 5.1 Analysis Dates and Days

- Reference Start Date and Day 0

The reference start date is defined to be the date of the index procedure. The index procedure is defined as the time the first interventional access-related puncture (arterial) is established.

The reference start date is considered to be day 0.

- Last Participation Date

The Last Participation Date is defined as the last date the patient is seen (e.g. maximum of the last date of procedure date, discharge date, follow-up visit date, exit date, adverse event date, and laboratory test date).

- Last Participation Day

Last Participation Day = Last Participation Date – Reference Start Date

Note: Last Participation Day is used as censor day for Kaplan-Meier analysis.

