8.9 WITHDRAWAL CRITERIA AND PROCEDURES

The Investigator will make every attempt to follow the patients at each of the required assessment periods. The reason for the withdrawal will be documented on the appropriate case report forms and in the medical records for each patient who has withdrawn.

Patients may be withdrawn from the study for any of the following reasons:

- Patient Withdrawal
The patient may voluntarily withdraw from the clinical study at any time, without penalty or loss of benefits to which they are otherwise entitled.
- Physician Withdrawal
The Principal Investigator also has the right to withdraw a patient if s/he feels it is in the best interest of the patient to do so.
- Lost to Follow-up
If a patient cannot be reached for a follow-up visit, the Investigator will document the contact efforts made to the patient and/or effort to obtain hospital records in the appropriate electronic case report form. If the patient cannot be reached in any way, or misses a visit, the patient will be considered "unable to contact" for that time interval. After three (3) documented attempts to make contact prove unsuccessful, a certified letter will be sent to the patient's residence. If there is no response after the certified letter is sent, the patient will be considered "lost to follow-up."

In all cases of withdrawal (as described above), withdrawn patients will not undergo further study follow-up procedures after the time of study exit. A study patient that has been withdrawn from the study will not be replaced.

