## 6. DATA AND ANALYSIS CONVENTIONS

### 6.1 General Conventions

- For continuous variables, summary statistics will include number of observations, mean, median, standard deviation, minimum, maximum, and 95% confidence intervals (based on normal distribution) per table shells. Nonparametric techniques may be used if the data does not meet the assumptions of parametric tests.
- For ordinal data, the count and percentage of patients will be presented.
- For categorical and qualitative variables, summary statistics will include number of observations, percentage, and 95% Clopper-Pearson confidence intervals per table shells. In general, the denominator for the percentage calculation will be based on total number of patients with evaluable data for a specified time point unless otherwise specified. Patients with missing data will be excluded from the denominator.
- Survival analysis techniques will be used to analyze the time-to-event variables. Summaries will include the number of patients at risk, number of events, number of patients with the event, and Kaplan-Meier estimates at given time points. Patients without events will be censored at their last known event-free time point. If this event-free time point occurs after the analysis time point, the days to event variable will be set equal to the analysis time point so that the patient will be included in the analysis. For patients who did not have an event or early withdrawal and have not yet completed the analysis visit, they will be censored at their last participation date. Standard errors will be calculated using Greenwood's formula and SAS defaults will be used for confidence bands and transformations on  $S(t)$  for the confidence limits. Kaplan-Meier event rate plots will be presented via the cumulative hazard rate plotted against the days from implantation.

- [REDACTED]

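### SAP 5.1 and 6.1 give different Kaplan-Meier censoring dates for patients lost to follow-up, and the 5.1 date can count unobserved time as event-free

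*SAP*

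**What the plan says.** SAP 5.1 gives an intended meaning: "The Last Participation Date is defined as the last date the patient is seen". A parenthesis introduced by e.g. then supplies the only derivation, the "maximum of the last date of procedure date, discharge date, follow-up visit date, exit date, adverse event date, and laboratory test date". A note adds: "Last Participation Day is used as censor day for Kaplan-Meier analysis".

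SAP 6.1 states the general rule differently: "Patients without events will be censored at their last known event-free time point". It uses the last participation date for a narrower group: "For patients who did not have an event or early withdrawal and have not yet completed the analysis visit, they will be censored at" that date.

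Protocol 8.9 sets out how a patient becomes lost: "After three (3) documented attempts to make contact prove unsuccessful, a certified letter will be sent" to the patient's home, and then "If there is no response after the certified letter is sent, the patient will be considered" lost to follow-up. Loss is listed there with patient and physician withdrawal, and the section closes: "In all cases of withdrawal (as described above), withdrawn patients will not undergo further study follow-up procedures after the time of study exit". Protocol 8.10 makes loss to follow-up a reason for study exit. Protocol 8.8 says that a missed visit alone is not withdrawal and that contact is tried again at the next interval. SAP 7.1 has a Study Exit form completed.

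SAP 8.4.2 applies Kaplan-Meier to time to first heart failure re-hospitalization in the as-treated cohort. It also plans a re-hospitalization rate per patient-year, without defining the exposure time.

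**The concern.** A patient should leave the risk set when knowledge of their event status ends. A declaration of loss follows a period in which nobody could reach the patient. If that declaration supplies the exit date, a maximum that includes it overrides the last real assessment. The patient then stays in the risk set as event-free over a stretch in which a hospital admission could have gone unrecorded. The denominator grows and the numerator cannot, so the event rate moves down, in the device's favour.

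Reproducibility is also at stake. Two programmers could follow the SAP faithfully, one using the 5.1 note and the other 6.1, and produce different curves from the same data.

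**Working it through.** The plan gives no figure to reproduce: the sample size of 60 has no statistical justification and no loss rate is stated. The check is therefore the text, then the possible length of the gap, then its effect under stated assumptions.

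**1. The two rules for a lost patient without an event**

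| | SAP 5.1 | SAP 6.1 |
|---|---|---|
| Censor date | Last Participation Date | Last known event-free point |
| Who | Everyone (unconditional note) | Patients without events; last participation date only where there is no early withdrawal and the analysis visit is still pending |
| Derivation given | Maximum, including exit date | None |

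Because Protocol 8.9 treats loss as a kind of withdrawal, 6.1 read literally sends lost patients to the last known event-free point. The 5.1 note sends them to the maximum.

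**2. Possible length of the gap**

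Inputs: the analysis windows in SAP 5.2. If loss is discovered at a missed scheduled visit, with no contact in between, the shortest gap runs from the close of one window to the opening of the next:

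- 1 month to 6 months: 150 − 37 = 113 days
- 6 months to 1 year: 320 − 210 = 110 days
- 1 year to 2 years: 685 − 410 = 275 days
- 2 years to 3 years: 1050 − 775 = 275 days

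The contact attempts and the letter come on top. Under Protocol 8.8 the gap may span a further interval.

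**3. Mechanism, by hand**

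Assumed: 50 patients at risk at day 180, of whom 5 are never seen again and are exited after day 365; 10 events by day 365 among the other 45; no other censoring.

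- Censored when last seen: 10/45 = 22.2%
- Censored at exit: 10/50 = 20.0%

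This arrangement is unfavourable: every loss falls at one visit and is carried through the whole interval.

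For exposure over the first year, with the other 45 observed throughout:

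- Observed: 45 + 5 × 180/365 = 47.47 patient-years
- Credited: 47.47 + 5 × 185/365 = 50.0 patient-years
- Effect on a rate with the same event count: 1 − 47.47/50 = 5.1% lower

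**4. Simulation with losses spread over follow-up**

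From the documents: 60 patients (planned enrolment, so an upper limit for the as-treated cohort) and nominal visit days. Assumed: exponential time to first event with hazard 0.2 or 0.4 per year; 5%, 10% or 20% lost; last attended visit equally likely at day 30, 180, 365 or 730; exit 30, 90 or 365 days later, capped at day 1095; no event captured in the gap. There were 600 replicates per scenario, with each data set analysed both ways. Cells show the Kaplan-Meier event rate (%) censoring at last visit → at exit.

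| Lost, lag | 0.2/yr, 1 year | 0.2/yr, 3 years | 0.4/yr, 1 year | 0.4/yr, 3 years |
|---|---|---|---|---|
| 10%, 90 d | 18.5 → 18.3 | 45.6 → 45.3 | 32.7 → 32.3 | 69.5 → 69.2 |
| 20%, 90 d | 18.3 → 17.9 | 45.3 → 44.7 | 32.8 → 32.1 | 70.0 → 69.3 |
| 10%, 365 d | 18.0 → 17.4 | 45.3 → 44.0 | 33.3 → 32.1 | 70.2 → 68.6 |
| 20%, 365 d | 17.8 → 16.6 | 45.4 → 42.7 | 33.2 → 30.9 | 70.0 → 66.8 |

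The true three-year values are 1 − exp(−0.6) = 45.1% and 1 − exp(−1.2) = 69.9%. Censoring at the last visit recovers them to within simulation error.

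The largest difference at a lag of 30 or 90 days is 0.7 points (32.8 − 32.1 and 70.0 − 69.3). With 20% lost and a 365-day lag the differences are 1.2 and 2.3 points at one year, and 2.7 and 3.2 points at three years. In that last row, first events per patient-year fall from 0.203 to 0.187 (7.9%) and from 0.407 to 0.372 (8.6%). No scenario tested moved the estimate upward.

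**The case against.** A reader might infer that every lost patient is credited with event-free time, so that the curve is known to be biased. The documents do not support that, for four reasons.

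- The list in 5.1 is introduced by e.g. and sits under a definition based on being seen. An exit date fits that definition when the exit coincides with a visit, such as study completion or the one-month exit of patients without an implant.
- SAP 6.1, read literally, already censors lost patients where one would want.
- Neither document says how the exit date is set for a lost patient. It could be recorded as the last contact.
- Protocol 8.8 and 8.9 have the site pursue hospital records, and 8.8 also the primary care provider, so re-hospitalization status may be known after the last visit.

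Scale also matters. This is a 60-patient early feasibility study. The exact 95% interval around 10/50 is about 10% to 34%, far wider than any shift shown above. The only Kaplan-Meier analysis named is an additional one.

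All of this stands as a limit on size and certainty. It does not remove the conflict. SAP 6.1 gives no derivation of the last known event-free point, so the one computable censor date in the SAP is the 5.1 maximum, and the 5.1 note has no exception for withdrawals. The 110- to 275-day gaps also mean that a lag above 90 days is plausible after the first month, although records or interim contact could shorten it.

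**Conclusion.** The inconsistency is established: for patients lost to follow-up, SAP 5.1 and 6.1 give different censoring rules, and the 5.1 derivation can contradict its own definition. The bias is conditional. It arises only if the 5.1 rule is programmed, the exit is dated at the declaration of loss, and event status in the gap is unknown. It would then run downward for first heart failure re-hospitalization, and for the per-patient-year rate if that rate uses the same date.

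Under the assumed hazards and loss rates, the effect is at most about 0.7 points for lags up to 90 days, and 1.2 to 3.2 points with 20% lost and a one-year lag. Without frequent loss or a long lag it is likely to stay below 1 point.

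It would be wrong to extend this to the main endpoints. The 30-day MAE composite and the device, procedural and clinical success endpoints are analysed as counts and percentages and do not use the censor day.

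**What to change.** In SAP 5.1, let the exit date enter the maximum only if the patient was seen or contacted, or event status was otherwise ascertained, on that date. Otherwise use the last date with documented status: visit, contact, hospital record or laboratory test. State that this date is the last known event-free time point of SAP 6.1, so that one rule governs all patients without events. Use the same date to close patient-years in SAP 8.4.2.

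The cost is a short SAP clarification and one change to the derivation program, provided dates of contact and record checks are available in the study data. The downside is slightly less follow-up time and, if there are losses, a slightly less favourable event rate.
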